12.4 Assessment of Safety

All subjects that have received one dose of study treatment will be evaluable for safety. Adverse events will be continuously monitored. Safety assessments using the NCI-CTCAE version 5 will be performed as outlined in Section 7 of the Study Calendar.

12.5 Assessment of Efficacy

All subjects with measurable disease who have received at least one cycle of treatment and have their disease re-evaluated will be evaluable for assessment of iPFS, PFS, ORR, OS, and HRQol.

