OBJECTIVES	
Primary Objective
 
1.) Intracranial progression free survival (iPFS)
 
Secondary Objectives
 
1.) Overall response rate (ORR) 2.) Extracranial Progression free survival (PFS) 3.) Overall survival (OS) 4.) Toxicity of atezolizumab plus carboplatin and etoposide
 
Exploratory Objectives
 
1.) Explore circulating biomarkers in patients with SCLC brain metastases 2.) Explore patient-reported quality of life (QoL) 3.) Investigate the immune and genomic landscape of SCLC primaries that metastasized to the brain

STUDY DESIGN	Single arm, multicenter phase II trial for n=60 patients with untreated extensive stage (ES) small cell lung cancer (SCLC) and asymptomatic brain metastases.
KEY ELIGIBILITY CRITERIA (See Section 3 for full eligibility criteria)	
 • Histological confirmation of Small Cell Lung Cancer- Stage IV/Extensive Stage (SCLC) per Veterans Administration Lung Study Group (VALG). • Untreated, asymptomatic brain metastases • No prior systemic therapy for metastatic disease [a single cycle of chemotherapy (platinum/etoposide) with or without atezolizumab is allowed within 30 days prior to enrollment]
STATISTICAL CONSIDERATIONS	A Kaplan-Meier curve will graphically describe iPFS, PFS, and OS among patients treated by at least one cycle of Atezolizumab. Median survival, as well as 6-month iPFS and PFS, and 12-month OS will be estimated with their 95% confidence intervals (CI). The impact of patients' demographics and baseline clinical characteristics on survivals will be evaluated in the context of a Cox PH model. The ORR, the proportion of treated subjects with a complete or partial response, will be calculated with its 95% CI. The

	
association of ORR with patients' demographics and baseline clinical characteristics will be evaluated in a logistic regression model.
 
The quality of life of treated patients at baseline and during treatment will be summarized and the patients' demographics and baseline clinical characteristics on the change of the quality of life will be evaluated in a linear regression.

TOTAL NUMBER OF SUBJECTS	N = 63 eligible patients (60 evaluable)
ESTIMATED ENROLLMENT PERIOD	Estimated 22 months from lead site opening to accrual
ESTIMATED STUDY DURATION	Estimated 40 months

TABLE OF CONTENTS

Schema	6
1. Background and Rationale	7
2. Study Objectives and Endpoints	10
3. Eligibility Criteria	11
4. Subject Registration	15
5. Treatment Plan	15

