2.2 Endpoints

2.2.1 Primary Endpoint

- Intracranial PFS is defined as the time from Day 1 of treatment until the criteria for intracranial disease progression is met as defined by RANO-BM or death as a result of any cause, whichever comes first.

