12.2.1 Definition of Primary Endpoint

The primary endpoint of the study is intracranial progression free survival (iPFS), which is defined as the time from Day 1 of protocol treatment until the criteria for iPFS is met as defined by RANO-BM or death from any cause, whichever comes first.

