12.2.2 Definition of Secondary Endpoints

ORR is the proportion of patients whose best response to protocol treatment are either complete response (CR) or partial response (PR) by the investigator using RECIST 1.1. Patients not meeting these criteria, including patients without any post-baseline tumor assessment, will be considered non-responders.

PFS is defined as the time from Day 1 of protocol treatment until the criteria for disease progression (intracranial or extracranial) is met as defined by RECIST 1.1 and RANO-BM, or death from any cause, whichever comes first. Subjects who have not progressed will be right-censored at the date of the last disease evaluation. If progression occurs in either intracranial or extracranial or both compartments, the criteria for progression-free survival will have been met per RANO-BM.

OS is defined as the time from Day 1 of protocol treatment until death from any cause.

CTCAE V5 will be utilized to define the grade and type of toxicities and adverse events.

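### Section 12.5 removes treated patients who die before any re-evaluation from iPFS, PFS, OS and ORR, which favours the treatment and conflicts with the synopsis and 12.2.2

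*Combined protocol and SAP*

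**What the plan says.** - **Section 12.5** defines who counts for efficacy: "All subjects with measurable disease who have received at least one cycle of treatment and have their disease re-evaluated will be evaluable" for iPFS, PFS, ORR, OS and quality of life. It does not say what re-evaluation means. In the Study Calendar (Section 7, note 5) the first repeat imaging falls before Cycle 3 Day 1, about week 6.
- **Endpoint definitions.** Section 2.2.1 ends the iPFS definition with "or death as a result of any cause, whichever comes first". Section 12.2.1 agrees: time runs "until the criteria for iPFS is met as defined by RANO-BM or death from any cause". Section 12.2.2 likewise makes death from any cause an event for PFS and OS.
- **Synopsis, Statistical Considerations:** "A Kaplan-Meier curve will graphically describe iPFS, PFS, and OS among patients treated by at least one cycle of Atezolizumab". For response it uses "The ORR, the proportion of treated subjects with a complete or partial response". Neither statement requires re-evaluation.
- **Section 12.2.2 on ORR:** patients who do not meet the response criteria, "including patients without any post-baseline tumor assessment, will be considered non-responders". On PFS: "Subjects who have not progressed will be right-censored at the date of the last disease evaluation". No matching censoring rule is written for iPFS.
- **Section 12.3** sizes the trial on 60 treated patients (median iPFS 5.2 against 4.0 months, one-sided level 0.15, power about 81%). It assumes 5% dropout before treatment, yet says 63 will be treated. The synopsis gives 63 eligible, of whom 60 are evaluable.
- **Sections 12.6 and 12.7** name no analysis population, so nothing overrides 12.5.

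**The concern.** Whether a patient is re-evaluated depends on surviving long enough, so 12.5 selects the population on the outcome. A patient treated for one cycle who dies in week 5 has a complete iPFS, PFS and OS record, and no scan is needed to classify it. Section 12.5 nevertheless takes that patient out of both numerator and denominator. For OS, which needs only a date of death, the condition has no purpose.

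The concern is limited to deaths before any re-evaluation. A progression seen on an early scan is itself a re-evaluation and stays in. A patient examined and found worse may also count as re-evaluated, because the RANO-BM table in 9.2.5 lists worse clinical status as progression.

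In a randomised trial both arms would lose such patients. Here the comparator is a fixed 4.0-month median, so the loss is one-sided. The estimates, the false-positive rate and the futility rule in 12.7 are all affected. Because 12.5 and the synopsis describe different sets, the plan also leaves room to settle the primary population after the data are seen.

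**Working it through.** **1. Reproduce the plan's power.** Inputs from 12.3: exponential survival, medians 4.0 and 5.2 months, 60 patients, 22 months' accrual plus 12 months' follow-up, one-sided 0.15. The plan says only that a logrank test is used.
- Log-hazard approximation with 58 events: Φ(√58 × ln(5.2/4.0) − 1.036) = Φ(7.616 × 0.2624 − 1.036) = Φ(0.962) = 0.832.
- One-sample log-rank, exact-variance formula: 0.803. Simulation: 0.815.
- Two-sample log-rank with 58 events: 0.485, which does not fit.

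The stated 81% therefore corresponds to a one-sample log-rank test, which is used below.

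**2. Effect of removing early deaths.** True median 4.0 months; Z = (E − O)/√E; 40,000 simulated trials per setting (standard error about 0.002). Exactly k patients with an event before week 6 (42/30.4375 = 1.38 months) are removed at random. The futility look is at the 29th event, stopping if one-sided p > 0.50. Apparent median = −ln(0.5 × (1 − k/60)) × 4.0/ln 2. Apparent 6-month iPFS = 0.354/(1 − k/60).

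| Removed of 60 | Rejection | Rejection, futility applied | Stopped for futility | Apparent median (months) | Apparent 6-month iPFS |
|---|---|---|---|---|---|
| 0 | 0.138 | 0.125 | 51.9% | 4.00 | 35.4% |
| 1 | 0.161 | 0.148 | 48.2% | 4.10 | 36.0% |
| 2 | 0.194 | 0.180 | 43.0% | 4.20 | 36.6% |
| 3 | 0.227 | 0.214 | 38.8% | 4.30 | 37.2% |
| 5 | 0.305 | 0.294 | 29.3% | 4.50 | 38.6% |
| 6 | 0.346 | 0.336 | 25.3% | 4.61 | 39.3% |

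With nobody removed, stopping at 52% agrees with the 50% chance claimed in 12.7. A second test form, ln(E/O) × √O, gives the same rejection rates to within 0.001. Removing an expected share instead of an exact count gives 0.167 at 2%, 0.184 at 3%, 0.223 at 5% and 0.342 at 10%.

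**3. Does the 63/60 margin help?** With 63 treated and 3 early deaths removed, so that 60 are analysed, rejection is 0.223 against 0.137 with none removed. With futility applied it is 0.209 against 0.123. Futility stopping is 39.2% against 52.0%. The margin restores the count and leaves the bias.

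**4. How many might be removed?** The documents give no early-death rate. For scale only, put a constant hazard on the OS medians quoted in Section 1.2 (10.3 and 12.3 months, from a trial in which 9% had brain metastases): P(death before t) = 1 − exp(−ln 2 × t/median).

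| OS median | Before day 21 (0.69 months) | Before week 6 | Day 21 to week 6 |
|---|---|---|---|
| 10.3 | 4.5% (2.7 of 60) | 8.9% (5.3) | 4.3% (2.6) |
| 12.3 | 3.8% (2.3) | 7.5% (4.5) | 3.7% (2.2) |

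If one cycle means a completed cycle, the synopsis set may also lose deaths before day 21. The last column is then what the re-evaluation clause alone removes. Restricting removals to that window, 2 or 3 removed gives rejection of 0.192 or 0.218, or 0.179 and 0.205 with futility applied.

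**5. ORR.** With an assumed 42 responders and 3 treated patients never re-evaluated, 12.2.2 gives 42/60 = 70.0% and 12.5 gives 42/57 = 73.7%.

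**The case against.** The strongest reply is that the undefined word carries the whole effect. A physical examination with a full neurological assessment is scheduled on Day 1 of every cycle, and 9.2.5 uses clinical status. If that counts as re-evaluation, anyone seen at Cycle 2 Day 1 qualifies. Those lost would be mainly deaths before day 21, whom the synopsis may drop too, so the clause would add close to nothing. That reading is possible. It is not the natural one, and leaving it open is itself a defect.

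Other points, and what stands:
- **ORR.** The specific rule in 12.2.2 could be taken to prevail, in which case ORR is not inflated. The two sections still contradict each other.
- **Size.** The larger figures (5 or 6 removed) may include patients the synopsis set also excludes; the clause alone points to 2 or 3. The early-death rate is borrowed from a different population. Both are fair.
- **Interim.** Applied at the interim, 12.5 also drops living patients not yet at week 6, whose event-free time favours treatment. Allowing for this, stopping with 1, 2, 3, 5 or 6 removed is 51, 46, 41, 31 or 28%. That is about 2 to 3 points higher than the table, with the same direction; for one removal it is essentially unchanged from 52%.
- **Estimation.** Section 2.1.1 is framed as estimation, and for 1 to 3 removals the median moves by only 0.1 to 0.3 months. But the target gain is 1.2 months, and 12.3 and 12.7 both rest on a test.

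**Conclusion.** The concern holds. As written, 12.5 excludes treated patients because they died early, against the definitions in 2.2.1, 12.2.1 and 12.2.2 and the population in the synopsis. The direction of the bias in the final analysis is certain. Its size depends on how many treated patients die before re-evaluation, on reading re-evaluation as imaging, and on a one-sample log-rank test with exponential survival. For the 2 or 3 removals that the scale calculation attributes to the clause alone, the false-positive rate is about 0.19 to 0.22 (0.18 to 0.21 with futility applied) against a planned 0.15. With one removal it stays about nominal. This must be fixed because it affects the primary endpoint, the error rate and the stopping rule.

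**What to change.** Replace 12.5 with: *iPFS, PFS, OS and ORR are analysed in all eligible subjects who receive at least one dose of study treatment; no post-baseline assessment is required.* The measurable-disease condition can go, since inclusion criterion 5 already requires a measurable brain metastasis. Then state that:
- a death before re-evaluation is an event on the date of death;
- intracranial progression that meets RANO-BM by clinical worsening (9.2.5) is an iPFS event on its date, even without a scan;
- only subjects with no post-baseline disease assessment of any kind, no documented progression and no death are censored at Day 1 for iPFS and PFS; they are followed for OS and counted as ORR non-responders;
- other event-free subjects are censored at the last disease evaluation, extending the existing PFS rule to iPFS.

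Use the same set for the interim in 12.7. Align the one-cycle wording in the synopsis and the 63/60 statements in 12.3 and the synopsis. Keep the re-evaluated set as a sensitivity analysis only. Quality-of-life change may use subjects with a baseline and at least one later questionnaire.

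The cost is protocol and SAP wording, with no extra patients, visits or scans. Reported medians and ORR may be slightly less favourable, and an ineffective regimen is more likely to be stopped.

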12.6 Data Analysis Plans

12.6.1 Analysis Plans for Primary Objective

Median iPFS and 6-month iPFS rate along with their 95% confidence intervals (CIs) will be estimated using Kaplan-Meier (KM) approach. KM curve will be used to characterize iPFS. Cox proportional hazard models will evaluate the relationship between iPFS with the patients' baseline characteristics, including age at enrollment, gender, race, and ECOG Performance Status and the estimated HRs and their 95% CIs will be provided.

12.6.2 Analysis Plans for Secondary Objectives

ORR and its 95% CI will be estimated.

Median PFS and OS and their 95% CIs will be estimated using Kaplan-Meier approach. KM curves will be used to characterize PFS and OS. Six-month PFS and 12-month OS rates and their 95% CIs will also be estimated. Cox proportional hazard models will evaluate the relationship between PFS or OS with the patients' baseline characteristics, including age at enrollment, gender, race, and ECOG Performance Status and the estimated HRs and their 95% CIs will be provided.

The types and frequencies of toxicities will be summarized by the severities.

12.6.3 Analysis Plans for Exploratory Objectives

The summary statistics (mean, standard deviation, median, Q1, Q3, and range) of subscale and overall scores derived from FACT-BR questionnaires will be calculated.

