1.4 Rationale

The IMpower133 clinical trial evaluated chemotherapy and atezolizumab for first line treatment of patients with untreated ES SCLC. The results from the trial led to an FDA approval and established this regimen as a new standard of care. However, while patients with brain metastases were allowed, prior cranial radiation was required for these patients. Furthermore, only 9% of enrolled patients had brain metastases. There remains an urgent need to define clinical outcomes for patients treated with chemotherapy and atezolizumab with asymptomatic, untreated brain metastases.

Recent studies with systemic immunotherapy in brain metastases patients have demonstrated that outcomes for patients with and without brain metastases are generally similar. The IMpower133 study demonstrated PFS outcomes of 5.2 months for the atezolizumab arm versus 4.3 months for the placebo arm. Thus, we hypothesize that atezolizumab plus chemotherapy (i.e. carboplatin and etoposide) will improve intracranial progression free survival (iPFS) in patients with brain metastases from SCLC relative to historical controls (\geq 5.2 months vs. 4 months).

This study will enroll patients with asymptomatic brain metastases and untreated ES SCLC. Patients will be treated with combination carboplatin, etoposide, and atezolizumab. Restaging radiographic imaging will occur every 6 weeks (approximately every 2 cycles of treatment). At time of progression, patients can pursue standard of care treatment and radiation therapy off study. Our hypothesis is that the addition of atezolizumab will improve intracranial progression free survival in patients with untreated brain metastases. Furthermore, the study will provide valuable insight in the clinical outcomes of the patient population with ES SCLC and brain metastases. In general, chemotherapy response rates are expected to be high, and immune checkpoint therapy is known to have efficacy in other CNS malignancies. We believe treatment with systemic therapy alone will 1) delay time to WBRT 2) preserve quality of life longer 3) allow a subpopulation of patients to avoid WBRT and 4) be able to avoid a detrimental impact on survival given the close radiographic follow up.

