7. STUDY CALENDAR & EVALUATIONS

Study Evaluation Cycle = 21 days	Screening	On Treatment Cycles 1-4			Maintenance Cycles 5+	Safety follow up visit	Long-term Follow up
	-28 days	Day 1 ± 2 days	Day 2	Day 3	Day 1 ± 2 days	30 days post last dose + 7 days	Every 3 months (±14 days)
REQUIRED ASSESSMENTS							
Informed Consent	X						
Medical History	X						
Physical Exam	X	X			X	X	
Vital signs and ECOG Performance Status	X	X			X	X	
Quality of Life Questionnaires		x ³			x ³	x ³	
AEs & concomitant medications	X	X			X	X	
LABORATORY ASSESSMENTS							
Complete Blood Cell Count with diff (CBC)	X	x ⁹			X	X	
Comprehensive Metabolic Profile (CMP)	X	x ⁹			X	X	
PT/INR and aPTT	X						
Thyroid Function Testing	X	C3D1			x ⁴	X	
Hepatitis Testing	X						
Pregnancy test (serum or urine) (WOCBP)	X	x ⁴			x ⁴		
DISEASE ASSESSMENT							
CT of chest	x ⁵	C3D1			x ⁵		x ⁵
CT or MRI of abdomen and pelvis	x ⁵	C3D1			x ⁵		x ⁵
MRI Brain	x ⁵	C3D1			x ⁵		x ⁵
TREATMENT EXPOSURE							
Atezolizumab		D1			x ⁶		
Carboplatin		D1					
Etoposide		D1-D3					
SPECIMEN COLLECTION							
Archival Tumor Tissue	x ⁷						
Blood Samples		x ⁸				x ⁸	
FOLLOW-UP							
Survival Status, Subsequent Therapy							X

- 1: Medical History; other data to be obtained during this assessment includes a smoking history questionnaire and trial awareness question. In addition, prior anti-cancer treatment should be documented including medications (chemotherapy, checkpoint inhibitors, etc) radiation or surgery. In addition, diagnosis and staging to include pathology report and TNM staging documentation. Histological confirmation per VALG of Stage IV Stage Small Cell Lung Cancer (SCLC)- extensive stage. Prior genomic testing (ie NGS) and PD-L1 results are required if available.
- 2: Physical exam to include a complete neurological exam. Vital signs to include temperature, pulse, respirations, blood pressure weight, and height (screening only) and ECOG performance status.
- 3: Quality of life evaluations include FACT-Br, FACIT-Fatigue, and Godin Leisure-Time Exercise Questionnaire. Questionnaires to be completed Cycle 1 Day 1 then every other Cycle of treatment (6 weeks; \pm 1 week) and at the D30 Safety Visit.

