8.6 Quality of Life Assessment

8.6.1 Patient Reported Outcomes

Quality of life evaluations include FACT-Br, FACIT-Fatigue, and Godin Leisure-Time Exercise Questionnaire. These questionnaires are to be completed Cycle 1 Day 1 then every other Cycle of treatment (6 weeks; ± 1 week).

Patient-reported Quality of Life (QoL) outcomes will be assessed using the following standardized and validated questionnaires:

- Functional Assessment of Cancer Therapy-Brain (FACT-BR) scale (version 4) [26], which contains subscales for physical (7-items), functional (7-items), emotional (6-items), and social/family (7-items) well-being, as well as a 23-item brain cancer subscale (BCS) that assesses symptoms commonly reported by brain cancer patients
- Functional Assessment of Cancer Therapy-Fatigue (FACIT-Fatigue) subscale (version 4) [27]
- Godin Leisure-Time Exercise Questionnaire Short Scale [28, 29], a simple questionnaire to assess patterns of exercise behavior during a subject's leisure time

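### Quality-of-life summaries rest almost wholly on patients still on treatment, with no method for dropout, so visit means can overstate how well quality of life is preserved; separately, the change regression does not name the baseline score

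*Combined protocol and SAP*

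**What the plan says.** Section 12.6.3 is the whole quality-of-life (QoL) analysis in the statistical section. It plans summary statistics "of subscale and overall scores derived from FACT-BR questionnaires will be calculated". It names no time points, model, completion report or rule for missing forms.

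The synopsis goes further: "The quality of life of treated patients at baseline and during treatment will be summarized". It also plans to relate change to patient characteristics: "demographics and baseline clinical characteristics on the change of the quality of life will be evaluated in a linear regression". The baseline QoL score is not among the covariates named, and 12.6.3 does not carry this regression over.

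On collection, footnote 3 of the Section 7 calendar says "Questionnaires to be completed Cycle 1 Day 1 then every other Cycle of treatment", "and at the D30 Safety Visit". Section 8.6.1 gives the on-treatment schedule ("These questionnaires are to be completed Cycle 1 Day 1 then every other Cycle of treatment") and does not mention the D30 form. Section 6.4 ends protocol therapy at RECIST 1.1 progression, among other reasons. Under calendar footnote 11, follow-up after progression is for survival. Section 12.5 limits the set evaluable for quality of life to patients with measurable disease, at least one cycle and a disease re-evaluation.

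QoL is exploratory (2.1.3). Section 1.4 nevertheless lists "2) preserve quality of life longer" among four expected benefits of systemic therapy alone.

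**The concern.** Apart from one D30 form, a patient stops contributing when treatment stops, and treatment stops largely because of progression or toxicity. The mean at a later visit therefore describes a shrinking and probably healthier subset. Section 12.5 also removes the earliest failures. With no control arm, the within-arm course is all the trial will have to say about QoL. A flat line of means from about half the patients, shown without the number of forms behind it, could be read as preserved QoL.

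The regression raises a separate question. A change score is correlated with its own baseline. Without the baseline score in the model, residual variance is larger than it need be, and covariate effects are open to regression to the mean.

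**Working it through.** The documents give no SD, effect size or completion rate for QoL, so there is no stated figure to reproduce. The inputs from the plan are the exponential model and the two iPFS medians in 12.3 (4.0 and 5.2 months; 5.2 is also the PFS quoted in 1.2), the 60 treated patients, and the 6-week form schedule.

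**Step 1: patients remaining.** Share event-free = exp(−ln 2 × t / median), with t in months = weeks × 7 / 30.4375. Week 24 is 5.52 months.

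| Week | Median 5.2: share (of 60) | Median 4.0: share (of 60) |
|---|---|---|
| 6 | 83% (50) | 79% (47) |
| 12 | 69% (42) | 62% (37) |
| 18 | 58% (35) | 49% (29) |
| 24 | 48% (29) | 38% (23) |

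These are approximate upper bounds for on-treatment forms, because extracranial progression and toxicity also end treatment.

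**Step 2: bias of a visit mean, closed form.** Suppose QoL has correlation ρ with time on treatment (assumed). The mean among those remaining is then too high by ρ × φ(q) / P, where P is the share remaining and q the matching normal cut-point. At week 24 with P = 0.479, φ(q)/P is about 0.83. This gives 0.3 × 0.83 = 0.25 SD and 0.5 × 0.83 = 0.42 SD.

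**Step 3: bias by simulation.** There were five visits to week 24, the step 1 retention for a 5.2-month median, a true decline of 0.40 SD, and dropout log odds of 0.5 to 1.0 per SD. All of these except retention are assumed. Between-visit correlation was also varied, and dropout followed either the last recorded score or the current, unseen one. Week-24 bias:

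- Visit mean of remaining patients against the baseline mean of all patients: +0.07 to +0.42 SD.
- Within-patient change among those remaining: −0.12 to +0.14 SD.
- Likelihood-based repeated-measures estimate: about 0 when dropout follows the last recorded score, and +0.07 to +0.22 SD when it follows the unseen one. It was less biased than the visit mean in every setting.

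**Step 4: direction.** A second simulation tied time on treatment to each patient's QoL slope. The true change at week 24 was −0.28 SD. The on-treatment summary showed −0.41, −0.28, −0.14, −0.05 and +0.05 SD for correlations of −0.3, 0, 0.3, 0.5 and 0.7. At zero correlation there is no bias, and at a negative one QoL looks worse than it is. Under this mechanism paired change moves with the visit mean, so how far it is affected depends on why patients leave.

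**Step 5: the baseline score.** With equal variances and baseline-to-follow-up correlation r, the variance of change is 2(1 − r) and the variance after baseline adjustment is 1 − r². The ratio is (1 + r)/2. For r = 0.7 it is 0.85, a 15% cut; for r = 0.3 it is 0.65, a 35% cut.

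**Step 6: does omitting the baseline score cause the dropout bias?** With a true change of −0.20 SD:

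| Dropout | Change, no baseline score | Change, with baseline score |
|---|---|---|
| None | −0.20 | −0.20 |
| Depends on baseline score | −0.30 | −0.20 |
| Depends on current score | −0.09 | +0.02 |

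It does not. In the second row the omission makes QoL look worse, and in the third, adding the score does not remove the bias.

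**The case against.** The strongest case for leaving the plan alone is that QoL is exploratory and that 12.3 says power for exploratory analyses is not a concern. The expectation in 1.4 is also stated relative to whole brain radiotherapy; with no such arm, no QoL model can test it. Describing treated patients during treatment is a legitimate summary if labelled as such. All of this stands, and it keeps the point minor. It does not answer the absence of completion numbers or of any handling of dropout.

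A second objection also stands in part. A repeated-measures model does best when dropout depends on recorded scores. When dropout followed the unseen current score (between-visit correlation 0.7, decaying over time), its estimate was biased by +0.11 to +0.23 SD, more than the paired change among those remaining (+0.06 to +0.12 SD). It also implicitly models scores after death. It improves on visit means but does not cure the problem.

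A reader might infer four stronger things that the documents do not support:

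- *The stated method necessarily biases QoL upward.* The direction rests on an assumed link between QoL and leaving treatment.
- *The missing baseline score produces the dropout bias.* Step 6 shows that these are separate matters. The score is also unnamed in a synopsis sentence, not excluded.
- *No off-treatment form exists, or D30 will not be collected.* The calendar requires it; the silence in 8.6.1 is editorial.
- *Section 12.6.3 restricts the tables to patients on treatment, visit by visit.* It does not say so. That is a natural reading of the synopsis together with the form schedule.

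**Conclusion.** The point holds as a minor one. The plan summarizes FACT-Br scores without a completion report, a longitudinal model or a missing-form rule, while its own medians leave 48% or 38% of patients event-free at week 24. If sicker patients leave first, raw week-24 means can overstate preserved QoL by roughly 0.1 to 0.4 SD. That size rests on assumed dropout log odds of 0.5 to 1.0 per SD and on assumed correlations, and it should not be quoted for within-patient change, whose bias can take either sign.

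The unnamed baseline score is a second, independent weakness. It costs 15% to 35% of the residual variance under assumed correlations of 0.7 to 0.3, and it leaves covariate effects open to regression to the mean.

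**What to change.** 1. Keep the descriptive tables. At each visit show forms expected and received, with reasons for missing forms, including progression and death.
2. Add to 12.6.3 a likelihood-based repeated-measures model of FACT-Br scores over a fixed set of on-treatment visits (for example through week 24), with visit and baseline score. Name a simpler covariance in case an unstructured one cannot be estimated. Report the D30 form separately, since it falls at a different time for each patient.
3. Keep the synopsis regression on demographics and clinical characteristics, carry it into 12.6.3 and add the baseline QoL score. The model in item 2 does not answer the covariate question and should not replace it.
4. State that the model assumes missingness is explained by observed scores and that results describe patients while alive. Add one sensitivity analysis for dropout that depends on unobserved scores.
5. Align 8.6.1 with calendar footnote 3 on the D30 form (editorial).

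The cost is SAP wording and modest extra analysis. The calendar already schedules every form needed. The remaining downside is the missing-at-random assumption: the model reduces the bias in visit means but does not fully remove it if dropout depends on the unseen current score.
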